14.3.8 OTHER SAFETY ANALYSES

Echocardiography findings will be summarized by dose group at baseline and at Cycles 3, 5, and the end of Cycle 6 or Early Termination.

Physical exam findings will be summarized by dose group at baseline, at the start of each cycle and at the End of Study or Early Termination.

ECOG performance status will be summarized at each visit where it is collected.

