	
replaced in the Monotherapy period, in Cycle 1 or 2, the number of patients will be higher than 34.
 
Analysis sets:
 
There will be two analysis sets
 
• Safety Set: All patients treated with at least one dose of idronoxil will be included in the Safety Set (SS). All analyses of safety, toxicity, and PK will be performed for this set.• Full Analysis Set (FAS): All patients who completed at least one cycle of combination therapy (at any NOX66 dose). 
Analyses of efficacy, tolerability, and biomarkers will be performed for the FAS. Separate summaries may be provided for patients participating in the Dose Escalation and Dose Expansion parts.
 
Safety (Primary analysis):
 
The safety profile will be based on Serious Adverse Events (SAEs), Treatment Emergent Adverse Events (TEAEs), standard clinical laboratory parameters (clinical chemistry, hematology, urinalysis), vital signs measurements, ECG parameters, and physical examination findings.
 
Adverse events (AE) will be coded using the Medical Dictionary for Regulatory Activities and summarized by dose when NOX66 is given alone or in combination with doxorubicin. The number and percentage of patients reporting TEAEs will be calculated overall, by system organ class, and by preferred term for each dose level. Adverse events will also be graded for severity according to the National Cancer Institute Common Terminology Criteria for Adverse Events, Version 5.0.
 
Serious Adverse Events (SAEs) will be summarized separately.
 
Cardiac AEs (including clinically significant abnormalities in ECG rhythm and waveform morphology reported as TEAEs) and changes in echocardiographic parameters will be summarized.
 
Descriptive statistics will be provided for demographics, baseline characteristics, and exposure to treatment by cohort.
 
Univariate summary statistics will be provided by dose group at each visit for quantitative laboratory parameters and vital signs and for the change from baseline in these parameters. For laboratory values and vital signs with defined CTC grades, shift tables will be provided for CTC grades from baseline to end of study and from baseline to worst value on study.
 
Univariate summary statistics will be presented for ECG parameters for the value at each measurement time point and the change from baseline to each measurement time point. A similar analysis will be provided for the worst value of each ECG parameter on study.
 
Findings from physical examinations and ECOG performance status will be summarized by dose of NOX66 given alone or in combination with doxorubicin.
 
Pharmacokinetics (Secondary analysis):
 
Individual blood concentration-time data and blood PK parameters will be summarized using descriptive statistics by dose and sampling time for idronoxil and metabolites. Separate summaries will be provided for PK

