10.2.3 DOSE MODIFICATIONS

The dose of doxorubicin can be reduced from 75 to 60 mg/m² if a Grade 2 toxicity related to doxorubicin occurs. If serum bilirubin is 1.2-3.0 mg/dL prior to a cycle, a 50% dose reduction of doxorubicin is recommended. If serum bilirubin is 3.1-5.0 mg/dL prior to a cycle, a 75% dose reduction of doxorubicin is recommended.

If a perineal and/or anal rash develops (Grade 1-2), a topical hydrocortisone containing haemorrhoid cream/ointment and/or cutaneous cream should be used. For Grade 3-4 perineal and/or anal rash, NOX66 treatment should be delayed until the rash resolves to Grade 1 or completely. NOX66 should also be delayed if there is proctitis, rectal mucositis, or ulcer of Grade 2 or higher. Treatment may be resumed when toxicity decreases to Grade 1. Treatment with NOX66 should also be delayed in the presence of anorectal infections and may be resumed after they are resolved.

All dose delays for NOX66 and doxorubicin need to be discussed with the Medical Monitor.

For patients developing neutropenia, the following guidelines should be used for doxorubicin dose modification.

Toxicity	Recommended Dose Modification
ANC < 1,000	No doxorubicin administered; treatment cycle delayed
≥ Grade 3 neutropenic fever/infection	Approximately 60 mg/m ² doxorubicin
≥ Grade 4 neutropenia lasting longer than 1 week	Approximately 60 mg/m ² doxorubicin
Second incidence of either: 1) ≥ Grade 3 neutropenic fever/infection 2) Grade 4 neutropenia lasting longer than 1 week	Second dose reduction to 45 mg/m ²
Reversible Grade 3 neutropenia with fever/infection or Grade 4 ANC	Retreatment with doxorubicin at Investigator's discretion

Abbreviation: ANC = absolute neutrophil count

In the event of cardiac toxicity (e.g., if there is an absolute decrease in LVEF of >10% from the previous evaluation, or if the actual LVEF decreases to ≤40%) doxorubicin must be discontinued. Doxorubicin must also be discontinued if the patient develops Grade 3 or 4 left ventricular systolic dysfunction (symptomatic congestive heart failure).

Patients who discontinue doxorubicin after 4 cycles of treatment should complete the remaining 2 cycles of NOX66 as planned. If doxorubicin is discontinued prior to 4 cycles, NOX66 treatment may continue in consultation and agreement with the Medical Monitor.

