11.4.2.3 Cardiac Monitoring

A 12-lead ECG after 5 minutes of rest in the supine position will be obtained at Screening. In the Dose Escalation Cohort, triplicate 12-lead ECGs in close succession at least 1 minute apart will be obtained after 5 minutes of rest in the supine position at -0.75, -0.5 and -0.25 hours prior to administration of NOX66 and at 1, 2, 5, and 8 hours after the first dose of NOX66 monotherapy (Day 1).

On Day 7 of Monotherapy, 12-lead ECGs will be recorded performed in triplicate in the same manner and time points as on Day 1. In addition, Holter monitoring, will be conducted from 8 to 24 hours post NOX66. On Day 2 of Cycle 1, the same evaluation will be done before and after administration of NOX66, and Holter monitoring will be performed from 8 to 24 hours after NOX66 administration (Dose Escalation and Dose Expansion Cohorts). On Day 2 of Cycles 2 to 6, (combination of NOX66 and doxorubicin), triplicate 12-lead ECGs will be obtained after 5 minutes of rest in the supine position at -0.25 hours prior to and at 1, 2, 5 and 8 hours post morning dose of NOX66.

On days when serial ECG readings occur, before electrodes are removed after the initial reading, the electrode position is to be marked on the skin with indelible ink and the same electrode position used for all subsequent ECGs for each patient.

The following windows are acceptable for performing the ECGs:

- +/-5 minutes for pre-dose ECGs required at -0.75, -0.5 and -0.25 hours prior to NOX66 administration.
- +/-10 minutes for post-dose ECGs required at 1 hour and 2 hours after NOX66 administration.
- +/-15 minutes for post-dose ECGs required at 5 hours and 8 hours after NOX66 administration.

Echocardiography will be assessed at the start of Cycles 3, 5 and at the end of Cycle 6 (or Early Termination), and compared to baseline (Screening).

If clinically indicated, an additional echocardiograph will be done at Cycle 1 prior to the first dose of doxorubicin. All clinically significant findings that are not present at baseline should be reported as AEs.

Echocardiogram assessment can be performed 1 day prior to the scheduled visit day.

For any patient with an absolute decrease in LVEF of >10% from the previous evaluation, or if the actual LVEF decreases to ≤40%, or ≥ Grade 3 LV systolic dysfunction, doxorubicin must be discontinued and echocardiograms are to be performed at 6-month intervals in the post treatment phase.

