11.6.2.10 Months 6, 9 and 12 (from Cycle 1 Day 1)

- Assess tumor response with CT or MRI.
- Single 12-lead ECG will be obtained after 5 minutes of rest in the supine position.
- Administer questionnaires BPI-SF, EORTC QLQ-C30 and EORTC QLQ-FA12.
- Review and record concomitant medications. Restrictions on concomitant medications are to be removed compared to NOX66 monotherapy and Cycles 1 to 6.
- Assess and review AEs (Section [16](#)).
- Assess overall survival.

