Abbreviations: BNP = brain type natriuretic peptide; CT = computed tomography; ECOG=Eastern Cooperative Oncology Group; ECG=electrocardiogram; ENOX2 = Ecto-NOX disulfide-thiol exchanger 2; EOS=End-of-Study; ET=Early Termination; Mo = month; MRI = magnetic resonance spectroscopy; PK=pharmacokinetics; QOL = Quality of Life; WOCBP = women of childbearing potential

Note: For days not specifically designated on the schedule of assessments, the standard of care for the individual institution will be followed, any AEs and concomitant medications will be recorded on the eCRF.

† Blood samples for chemokines, cytokines, immunoassays (ENOX2) and genetic mutation to be collected either after eligibility is confirmed at Screening, or on Day 1 just prior to the first dose of NOX66.

#Dose Escalation Cohort only

*Dose Expansion Cohort only

Dose Escalation and Dose Expansion Follow-Up Period and End of Study/Early Termination						
Assessment	Study Day	Follow-Up (months from Cycle 1 Day 1)				EOS/ET ¹⁵
		6	9	12	15 ¹⁷	
Assess disease status (CT and/or MRI) ²		X	X	X		X
Vital signs						X
Physical examination						X
ECOG performance status						X
Hematology						X
Clinical chemistry						X
Urinalysis						X
12-lead ECG		X	X	X		
Record AEs ¹⁷		X	X	X	X	X
Prior and concomitant medications		X	X	X	X	X
Brief Pain Inventory (BPI-SF) ¹⁹		X	X	X		X
EORTC QLQ-C30 ¹⁹		X	X	X		X
EORTC QLQ-FA12 ¹⁹		X	X	X		X
Overall survival		X	X	X	X	X

1. Full medical and surgical history will be recorded at Screening. At Day 1 monotherapy; an interim history is to be recorded prior to first dose of NOX66.
2. Standard of care imaging performed prior to informed consent but within 28-days of enrollment may be used to confirm screening requirements. Disease status will be measured by radiologic methods (CT or MRI) at Screening, prior to beginning of Cycle 1 (only for dose escalation, if the previous scan is more than 28 days), end of Cycles 2, 4 and 6, at Months 6, 9 and 12 and End of Study. No patient is permitted to start a subsequent cycle until it is confirmed that disease progression has not occurred at the scheduled imaging assessment timepoint.
3. Vital signs will include weight, body temperature, respiratory rate, radial pulse rates, and systolic and diastolic blood pressures. Height and body surface area will be recorded at Screening only.

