14.3.5 LABORATORY SUMMARIES

Safety laboratory results will be summarized by dose group. At each scheduled laboratory collection, the laboratory result and the change from baseline in laboratory result will be summarized for each laboratory parameter. CTC grades will be assigned to laboratory results where they are defined, and the frequency and percentage of each CTC grade will be included in the summary.

Shift tables will be provided for change in CTC grade from baseline to end of study and from baseline to worst grade on study.

Brain type natriuretic peptide measurements will be summarized using descriptive statistics at baseline and at Cycles 1, 3, 5, and the end of Cycle 6 or Early Termination (if occurs prior to the end of Cycle 6). The number and percentage of patients with BNP laboratory values greater than 500 pg/mL and with BNP laboratory values between 100 and 500 pg/mL will be presented.

Blood levels of chemokines and cytokines will be summarized using descriptive statistics at baseline, Day 7 of Monotherapy period (only for Dose Escalation), at Cycle 3, and at the end of Cycle 6 or at Early Termination (if occurs prior to the end of Cycle 6).

Listings of genetic mutations at baseline and at end of Cycle 6 or Early Termination will be made.

Blood levels of ENOX2 will be summarized using descriptive statistics at baseline, at Cycle 3, and at the end of Cycle 6 or at Early Termination (if occurs prior to the end of Cycle 6). These levels will also be assessed in the same manner for patients in the Dose Escalation Cohorts, including those on Day 7 of Monotherapy period, if the samples are collected.

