14.3.7 ECG PARAMETERS

For each ECG parameter (PR, RR, QRS, and QT intervals, and QT interval corrected for heart rate using QTcF intervals where the QT intervals corrected for heart rate by Fridericia's formula [QTcF = QT/(RR)^{2/3}]), the parameter and the change from baseline in that parameter will be summarized at all time-points where an ECG is collected. Where triplicate ECG measurements are available, the descriptive statistics will be calculated using the arithmetic average of the three raw measurements. Holter monitoring will not assess ECG intervals but will provide information on cardiac rate and rhythms.

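### The conditional 6-monthly post-treatment echocardiograms in 11.4.2.3 are missing from the follow-up schedule and from 14.3.8, and LVEF has no lowest on-study value or count against the protocol's own criteria

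*Combined protocol and SAP*

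**What the plan says.** **The order.** Section 11.4.2.3 sets three triggers: an absolute LVEF drop of more than 10% since the preceding scan, an LVEF of 40% or lower, or left ventricular systolic dysfunction of Grade 3 or worse. For a patient who meets any of them, doxorubicin stops and "echocardiograms are to be performed at 6-month intervals in the post treatment phase".

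**The schedule.** The last panel of Table 4, titled "Dose Escalation and Dose Expansion Follow-Up Period and End of Study/Early Termination", has no echocardiography row. Footnote 18, the only echocardiography footnote to the table, covers a symptom-driven repeat before the first doxorubicin dose. The visit lists in 11.6.2.10 to 11.6.2.12 do not mention echocardiography, although the Month 6, 9 and 12 list names an ECG: "Single 12-lead ECG will be obtained after 5 minutes of rest in the supine position". The Synopsis schedule for echocardiography also ends at Cycle 6 or early termination.

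**The analysis.** For echocardiography, 14.3.8 states: "Echocardiography findings will be summarized by dose group at baseline and at Cycles 3, 5, and the end of Cycle 6 or Early Termination". ECG parameters, by contrast, "will be summarized at all time-points where an ECG is collected" (14.3.7), and 14.3.8 treats ECOG status the same way. For ECG the Synopsis adds: "A similar analysis will be provided for the worst value of each ECG parameter on study". Laboratory grades get shift tables to the worst grade. For BNP, 14.3.5 plans this count: "The number and percentage of patients with BNP laboratory values greater than 500 pg/mL", with a second band from 100 to 500 pg/mL.

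**The concern.** Section 11.1.1 lists echocardiographic change among the primary safety endpoints. Patients may receive up to 6 × 75 = 450 mg/m² of doxorubicin together with a new agent. Two basic questions follow: how many patients at each NOX66 dose met the protocol's own LVEF criteria, and whether their LVEF recovered.

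The tables as planned answer neither directly. A site that books visits from Table 4 could overlook the recovery scans. If the scans are done, 14.3.8 does not include them. A reader would have to assemble the answer from adverse event and withdrawal records. Disposition may help little, because 10.2.3 keeps some of these patients on NOX66: "Patients who discontinue doxorubicin after 4 cycles of treatment should complete the remaining 2 cycles of NOX66 as planned".

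**Working it through.** The plan gives no figure to reproduce here. The check sets the provisions side by side, then does calendar arithmetic and two constructed illustrations.

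**1. How the safety measures are treated**

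| Measure | Time points summarized | Worst on-study value | Threshold or grade count |
|---|---|---|---|
| ECG | wherever recorded (14.3.7) | yes (Synopsis) | none stated |
| Laboratory | each scheduled collection (14.3.5) | worst grade (Synopsis, 14.3.5) | by CTC grade |
| BNP | baseline, Cycles 1, 3, 5, end of Cycle 6 or ET | none stated | two bands (14.3.5) |
| ECOG | wherever recorded (14.3.8) | none stated | not applicable |
| LVEF | baseline, Cycles 3, 5, end of Cycle 6 or ET (14.3.8) | none | none |

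Section 14.3.1 says in general that all data are summarized, but 14.3.8 is the specific rule for echocardiography and its list is closed.

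**2. Scans per triggered patient up to Month 18.** Table 2 puts the end of Cycle 6 at 4.2 months after Cycle 1 Day 1 and End of Study at Month 18. The starting point is not stated, so both readings below are assumptions.
- Counted from the end of treatment after six cycles: (18 − 4.2)/6 = 2.3, so 2 scans, at 4.2 + 6 = 10.2 and 4.2 + 12 = 16.2 months. Neither coincides with a scheduled contact (Months 6, 9, 12, 15 and 18, with a 7-day window).
- Counted from the end of treatment for a patient stopped at the Cycle 3 Day 1 scan (42 days, about 1.4 months): (18 − 1.4)/6 = 2.8, so 2 scans, at about 7.4 and 13.4 months.
- Aligned with the visits counted from Cycle 1 Day 1: Months 6, 12 and 18, so 3 scans.

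Table 4 and the visit lists show none on any reading.

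**3. Can the planned statistics give a count?** Section 14.3.1 plans n, mean, SD, median, minimum and maximum. Both data sets below are invented; they show only what these statistics can and cannot determine. The 10% drop is read as 10 LVEF points.

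*n = 16 (expansion cohort size), change from Screening at one visit:*
- A: −24, −20, −18, −10, −10, −9, −9, −9, −7, −7, −5, −2, −2, 0, 2, 2
- B: −24, −16, −16, −13, −13, −12, −11, −11, −5, −5, −3, −2, −1, 1, 1, 2

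In each set the sum is −128, so the mean is −128/16 = −8.0. The sum of squares is 1882, so SD = √[(1882 − 16 × 64)/15] = √57.2 = 7.56. The median is (−9 − 7)/2 = −8 in A and (−11 − 5)/2 = −8 in B. Minimum −24 and maximum 2 are the same in both. Patients with a fall of more than 10 points: 3 in A, 8 in B. This counts falls from Screening, which is not the 11.4.2.3 criterion except where Screening is the preceding scan.

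*n = 3, fall since the preceding scan:* Screening LVEF is 60 in all three patients, Cycle 3 values are 60, 55, 50 (mean 55, SD 5) and Cycle 5 values are 55, 50, 45 (mean 50, SD 5). No patient meets a numerical criterion at Cycle 3, where the largest fall is 10 and the lowest LVEF is 50. At Cycle 5 the count depends on which patient has which value:
- 60→55, 55→50, 50→45: falls of 5, 5, 5, so 0 patients above 10.
- 60→45, 55→50, 50→55: falls of 15, 5, −5, so 1 patient above 10.

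Of the 6 possible pairings, 2 give one patient and 4 give none, with identical by-visit summaries.

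**The case against.** The strongest reply has four parts.

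- **The order binds anyway.** Section 11.4.2.3 is mandatory text, and 17.5 holds sites to the whole protocol. Section 11.6.2 allows extra follow-up visits for notable safety findings and doxorubicin toxicity, and 11.4.2 allows additional tests. This stands. A reader might infer that the scans will not be done or that these patients go unmonitored; the documents do not support that. The defect is a schedule that does not match the order, plus an unstated starting point.
- **Much is recorded elsewhere.** Clinically significant new findings are reported as adverse events (11.4.2.3), and the definition in 16.1.1 covers abnormal diagnostic results. Section 14.3.4 tabulates events by dose group, term and grade, with cardiac failure and cardiomyopathy queries. Section 14.3.3 summarizes doxorubicin dose changes, and 9.5 requires the reason for stopping either drug. So a reader who infers that a triggered patient would leave no trace goes too far. None of these, however, counts patients against the LVEF criteria or shows recovery.
- **The SAP may supply it.** Section 14.3.12 defers presentations to a separate SAP, which is not among the documents. It could contain every analysis item requested here, so their absence from the final analysis cannot be claimed. It cannot repair Table 4.
- **The examples are invented, and this is descriptive Phase I work.** True. At Cycle 3, with Screening as the preceding scan, the falls of more than 10 points in the n = 16 sets would also produce recorded doxorubicin stops. An LVEF of 40% or less at a summarized visit would show in that visit's minimum, though the minimum does not say how many patients reached it.

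**Conclusion.** The point holds as an inconsistency within the protocol and a gap in the summary of a listed primary safety endpoint. It should be corrected, but it does not threaten the design. The schedule mismatch is certain from the text. The analysis gap holds for the plan as written and is subject to the SAP.

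For each triggered patient, 2 or 3 ordered scans have no place in the follow-up schedule and no planned summary. The range rests on the two assumed starting points. The documents give no basis for estimating how many patients will be triggered. The constructed data sets show that by-visit statistics cannot determine the criterion counts; they do not predict how much information would be lost. The point does not depend on how long adverse events are followed.

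**What to change.** 1. **Protocol correction.** Add a conditional echocardiography row or footnote to the follow-up part of Table 4, in the manner of footnote 18, with matching entries in the visit lists. State what the 6 months count from, for example the end of treatment, or alignment with Months 6, 12 and 18.
2. **Section 14.3.8 or the SAP.** Summarize echocardiography on every occasion it is performed, including the symptom-driven repeat and the post-treatment scans.
3. **Section 14.3.8 or the SAP.** By dose group, report the lowest on-study LVEF with its change from Screening, and the number and percentage of patients meeting each numerical criterion: a drop of more than 10 points since the preceding scan, and an LVEF of 40% or lower. List LVEF over time for those patients.

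If the SAP already contains items 2 and 3, only item 1 remains. The cost is a line in Table 4, short visit-list entries and a few extra tables with small counts. Every scan is already ordered, and the doxorubicin stopping rule does not change.

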14.3.9 PHARMACOKINETIC ANALYSES

Blood concentration of idronoxil and metabolites will be summarized by collection time for each dose group using descriptive statistics. Separate summaries will be provided for idronoxil blood concentrations collected on Days 1 and 7 of idronoxil monotherapy, and from pre-dose to 4 hours post dose on Day 2 of Cycles 1 to 6. Trough values will also be assessed on Days 7 and 8 of Cycles 1, 3 and 5. Blood concentrations of idronoxil after monotherapy and in combination with doxorubicin will be compared.

Plasma concentrations of doxorubicin and doxorubicinol will be summarized by collection time for each dose group using descriptive statistics.

Pharmacokinetic parameters will be summarized by descriptive statistics for each dose group for idronoxil alone on Days 1 and 7. Graphical methods may be used to assess the relationship between idronoxil and doxorubicin concentrations and QTc values and other toxicities of interest.

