--	--

	
samples collected for single-dose administration, repeated administration, and administration in combination with doxorubicin.
 
Blood PK parameters will be determined by noncompartmental analysis for idronoxil and metabolites and will be summarized by dose and treatment day. Concentrations of idronoxil obtained in the presence of doxorubicin will be compared to monotherapy.
 
Concentrations of doxorubicin and doxorubicinol will be determined after the administration of the infusion in the presence of NOX66 and will be compared to historical controls.
 
The relationship between PK parameters and AEs and other safety findings may be assessed by graphical methods and special summary tables.

	
Efficacy (Secondary analysis):
 
The DCR, ORR, and the incidences of CR, PR, SD, and Progressive Disease (PD) as assessed by RECIST v1.1 criteria will be summarized for the MTD of the combination by counts and percentages and exact 95% confidence intervals at the end of Cycles 2, 4, and 6, at the 6-month, 9-month, and 12-month follow-up visits and at End of Study.
 
Survival functions will be computed for OS and PFS by the Kaplan-Meier method. Estimates of median OS and median PFS will be presented.

	
Quality of Life (Secondary Analysis):
 
Quality of Life analyses will be performed for the FAS. Scale measures from the EORTC QLQ will be presented by dose for each visit, along with change from baseline to each visit. Brief pain inventory items and fatigue parameters will be summarized by dose at each visit as well as the change from baseline to each visit.

	
Exploratory Analysis:
 
An exploratory analysis will be performed to assess various factors which may contribute to response to the combination of NOX66 and doxorubicin. These factors include, NOX66 dose or exposure, cytokine, chemokine and ENOX2 response, lipidomic profiling (capturing over 300 lipid species as determined by liquid chromatography-tandem mass spectrometry), histopathology, and specific genetic mutations. The acceptability of the suppository dosage form by patients will also be determined.

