8.1.1 DOSE-ESCALATION

For all dose escalation cohorts, there will be 7 days of monotherapy treatment with NOX66 followed by a 5- day washout period prior to the start of combination cycles of NOX66 and doxorubicin. The purpose of the monotherapy treatment is to evaluate the safety and tolerability of NOX66 when administered alone and as well as single and multiple dose PK of idronoxil.

The dose-escalation part of the study will include three planned Treatment Groups (800, 1200, 1800 mg daily) of 3 patients each. The first 3 patients will be entered at Dose Level 1 and will receive daily doses of NOX66 for 7 days. All of these doses, except for the 1800 mg have been evaluated in 2 previous clinical trials and have been relatively well tolerated as monotherapy for 14 days and in combination with carboplatin for 42 days.

After a rest period of 5 days and if no significant toxicities (DLT equivalent toxicity) have occurred, patients will enter the combination therapy part of the study which will consist of up to 6 x 21-day treatment cycles. Each cycle will consist of 7 days of NOX66 (at the assigned dose), doxorubicin (75 mg/m²) on Day 2 of the 21-day cycle (administered at approximately 1 hour after rectal application of NOX66) and a rest period of 2 weeks.

For the 800 mg and 1200 mg dose levels NOX66 will be administered twice-daily (BID) with a 400 mg or 600 mg suppository, respectively, and the 1800 mg dose level will entail administration of a 600 mg suppository three times daily (TID). In all cohorts, doxorubicin will be given initially at 75 mg/m² as an intravenous infusion over 15 minutes (or as per standard of care). This dose may be reduced to 60 mg/m², at the Investigator's discretion for unacceptable Grade ≥ 2 toxicity. A dose reduction of 50% is recommended if serum bilirubin is 1.2 -3.0 mg/dL prior to a cycle. If serum bilirubin is 3.1-5.0 mg/dL prior to a cycle, a 75% dose reduction of doxorubicin is recommended.

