8.3.4 DETERMINATION OF DLT

At the end of Cycle 1, all patients in each cohort will be evaluated for DLTs for dose escalation of the next cohort. During the other cycles, assessment of DLTs will be done on an ongoing basis, and if they arise, the doses of NOX66 or doxorubicin or both may be reduced. If a new DLT is most likely related to doxorubicin, the dose of doxorubicin should be reduced to 60 mg/m² or to 37.5 or 18.75 mg.m² (based on serum bilirubin) or delayed until toxicity has been resolved or improved. If the DLT is likely related to NOX66, the Investigator may lower the NOX66 dose and/or extend the dosing interval.

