14.3 STATISTICAL METHODOLOGY

14.3.1 GENERAL STATISTICS METHODS

All data will be summarized by idronoxil dose group. For safety analyses, a summary group consisting of all dose groups combined may also be presented.

For all measurements, the baseline value will be the last measurement taken before the first dose of study drug, whether idronoxil or of idronoxil + doxorubicin depending on the cohort.

Standard summary statistics will be presented for all measurements. For continuous variables, the standard summary statistics will be the number of observations (n), mean, standard deviation, median, minimum and maximum. For categorical variables, the standard summary statistics will be the number and percentage of observations in each category. Categories that are specified on the eCRF which contain no observations will be presented in the data summaries with a value of 0.

An AE with a completely missing start date will be assumed to start one minute after the date-time of the first idronoxil dose. If the severity of a reported AE is missing, it will be assumed that the event is severe; similarly, if the relationship of a reported AE to study treatment is missing, it will be assumed that the event is definitely related to treatment. No other missing data will be imputed. Incomplete start dates for Adverse Events and Concomitant Medications and incomplete end dates for AEs will have missing parts imputed by a conservative procedure which will be specified in the Statistical Analysis Plan (SAP).

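### Later-cycle doxorubicin concentrations are summarised by NOX66 dose group without regard to the doxorubicin dose given, so dose reductions and exposure changes are mixed

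*Combined protocol and SAP*

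**What the plan says.** The doxorubicin PK analysis in Section 14.3.9 is one sentence: "Plasma concentrations of doxorubicin and doxorubicinol will be summarized by collection time for each dose group using descriptive statistics". Section 14.3.1 fixes the grouping: "All data will be summarized by idronoxil dose group". The synopsis (Pharmacokinetics, secondary analysis) adds that doxorubicin and doxorubicinol concentrations measured in the presence of NOX66 "will be compared to historical controls". Section 11.1.2.1 plans comparisons of inter- and intra-patient variability across the study.

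The doxorubicin dose is not constant:

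- Section 8.1.1: in all cohorts, "doxorubicin will be given initially at 75" mg/m².
- Section 10.2.3: "The dose of doxorubicin can be reduced from 75 to 60" mg/m² for toxicity. The neutropenia table in that section then has "Second dose reduction to 45" mg/m².
- Section 10.2.3, bilirubin: "If serum bilirubin is 1.2-3.0 mg/dL prior to a cycle, a 50% dose reduction of doxorubicin is recommended", with a 75% reduction in the next band.
- Section 8.3.4 gives the bilirubin-reduced doses as 37.5 and 18.75 mg/m².

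Table 4, footnote 13, confirms that the Day 2 dose in any cycle may be a reduced one. Doxorubicin is sampled at 0.5, 4 and 6 hours after the infusion in Cycle 1. It is sampled at 0.5 and 4 hours in Cycles 2, 4 and 6, except that Section 11.4.3 omits the 0.5-hour sample at Cycle 4 in the escalation cohorts.

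**The concern.** A concentration measured after 37.5 mg/m² and one measured after 75 mg/m² enter the same cell of the table if the two patients share a NOX66 dose group and a sampling time. No section provides for dividing by the dose given, stratifying by it, or restricting to patients on the initial dose.

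The likely error has a direction. Section 11.1.2.4 says that more myelosuppression than doxorubicin alone would cause, or unexpectedly high AST, ALT or bilirubin, would suggest an additive effect of NOX66. Neutropenic events and raised bilirubin are also triggers for reducing doxorubicin in Section 10.2.3. If NOX66 raised doxorubicin exposure, the resulting toxicity would prompt reductions, and these would lower the later-cycle concentrations in which the rise might be seen.

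The protocol itself gives a reason to look. Section 10.4 notes that idronoxil may inhibit CYP3A4 in vitro, and it prohibits strong CYP3A4 inhibitors around doxorubicin treatment. That does not show an interaction, but it makes an interpretable doxorubicin summary worth having.

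What is at stake is the reading of the Cycle 2, 4 and 6 tables and of the within-patient comparison across cycles.

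**Working it through.** The plan states no figure on this point, so there is none to reproduce. The check uses the plan's dose levels and two assumptions: concentration is proportional to dose, and a stated share of patients is reduced. The documents give neither.

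**Step 1. Dose factors, k = dose given / 75.**

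- 60/75 = 0.80
- 45/75 = 0.60
- 75 × 0.50 = 37.5, so k = 0.50
- 75 × 0.25 = 18.75, so k = 0.25

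The last two agree with the doses in Section 8.3.4. The full range is 75/18.75 = 4-fold.

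**Step 2. Effect on a later-cycle group mean.** If a share f of the group is reduced, and those patients would otherwise have had the group's average concentration, the mean falls by f × (1 − k).

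| Share reduced | Dose (mg/m²) | Fall in mean |
|---|---|---|
| 1/3 | 60 | 1/3 × 0.20 = 6.7% |
| 1/2 | 60 | 1/2 × 0.20 = 10% |
| 1/6 | 37.5 | 1/6 × 0.50 = 8.3% |
| 1/6 | 18.75 | 1/6 × 0.75 = 12.5% |

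An escalation cohort may have only 3 patients. There, one patient at 37.5 lowers the mean by 1/3 × 0.50 = 16.7%, and one at 18.75 by 1/3 × 0.75 = 25%.

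**Step 3. Effect on a true exposure ratio.** Let R be the true ratio at equal doxorubicin dose, against a reference with no reductions. The observed ratio is R × [(1 − f) + f × k].

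| R | Share reduced | Dose (mg/m²) | Observed ratio |
|---|---|---|---|
| 1.25 | 25% | 60 | 1.25 × 0.95 = 1.19 |
| 1.25 | 50% | 60 | 1.25 × 0.90 = 1.13 |
| 1.25 | 100% | 60 | 1.25 × 0.80 = 1.00 |
| 1.25 | 50% | 37.5 | 1.25 × 0.75 = 0.94 |
| 1.5 | 50% | 60 | 1.5 × 0.90 = 1.35 |

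At moderate rates of step-down to 60 mg/m² the ratio is attenuated but still visible. It disappears or reverses only with frequent or deep reductions.

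**Step 4. Within one patient.** A reduction from 75 lowers the later concentration through dose alone by 1 − k: 20% at 60, 40% at 45, 50% at 37.5 and 75% at 18.75 mg/m². In the intra-patient comparison of Section 11.1.2.1 this would count as variability.

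**Step 5. Which cycles are touched.** Cycle 1 Day 2 is the first doxorubicin dose, so no reduction for doxorubicin toxicity can precede it. Only a bilirubin reduction before Cycle 1 could lower it. That would be unusual, because Section 9.2 requires bilirubin below the upper limit of normal at entry, but known Gilbert's disease is exempt and a NOX66 monotherapy period comes first in the escalation cohorts.

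**Step 6. After normalisation.** Dividing each concentration by the dose given removes k from the formula, so the observed ratio equals R for every f under proportionality.

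**The case against.** The strongest reply is that the best comparison is already intact. Cycle 1 Day 2 has the fullest doxorubicin sampling, comes before any reduction for doxorubicin toxicity, and is naturally separate because the summary is by collection time and Table 7 sets collection times out by cycle and day. This stands, and it confines the point to Cycles 2, 4 and 6. A reader might infer that the plan pools concentrations across cycles. The text does not say so, although Section 14.3.9 names cycles for idronoxil and not for doxorubicin.

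A reader might also infer that the historical-control comparison is biased low as planned. The synopsis does not say which cycles feed it. If Cycle 1 is used, this bias is essentially absent.

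The stakes are low. The PK objective in Section 7.2 concerns idronoxil, the synopsis calls the in-cycle sampling exploratory, and no test or decision rule uses these means. That also stands.

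Two further replies carry less weight. Section 14.3.3 will show final and cumulative doxorubicin doses and the number of dose changes, but in a separate summary that does not link a dose to a concentration. Section 14.3.12 leaves further methods to an SAP whose text is not in the combined document. That SAP may add normalisation, but nothing available shows that it will.

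Finally, raw concentrations are the right quantity for relating exposure to QTc or toxicity, which Section 14.3.9 also envisages. They should stay alongside the normalised values.

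**Conclusion.** The point holds for the later cycles. Followed as written, the Cycle 2, 4 and 6 summaries and the intra-patient variability comparison confound the doxorubicin dose given with doxorubicin exposure, and could understate a NOX66-related rise. The historical comparison shares the problem only if it includes later samples at reduced doses.

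The illustrative size is a fall of about 7% to 12.5% in a later-cycle group mean for the shares in Step 2, and more in a cohort of 3. These figures rest on proportional kinetics and on reduction shares that the documents do not give. If reductions fall on the patients with the highest exposure, the effect on the mean would be larger than shown.

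It is tempting to conclude that the plan would hide an interaction altogether. The arithmetic does not support that as a general statement: a true ratio of 1.5 still appears as 1.35 with half the patients at 60 mg/m², and Cycle 1 remains largely clean. Nor does the point reach the MTD, which rests on Cycle 1 DLTs. It is a minor but essentially free improvement to an exploratory analysis.

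**What to change.** Amend Section 14.3.9, or write into the SAP, the following:

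1. Summarise doxorubicin and doxorubicinol by NOX66 dose group, cycle and sampling time, as concentration divided by the doxorubicin dose given (per mg/m²), with raw concentrations alongside.
2. Base the historical-control comparison on Cycle 1 samples from patients given the initial dose, or on dose-normalised values with the historical data normalised in the same way. State which.
3. Use dose-normalised values for the doxorubicin part of the intra-patient variability comparison in Section 11.1.2.1.
4. State that normalisation assumes dose proportionality, and list the dose given beside each concentration so that a reader can check its influence.

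The cost is programming only. The cumulative-dose and dose-change summaries in Section 14.3.3 already require the administered doses to be recorded. No sample, visit, dose or clinical rule changes.
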